2. SYNOPSIS

Study Title	Neuroimaging Approaches to Deconstructing Acupuncture for Chronic Pain
Study Sponsor	National Institutes of Health, National Center for Complementary and Alternative Medicine Grant Number: R01AT007550
Study Objective	To evaluate the impact of acupuncture-induced somatosensory afference on altered neurobiology and analgesia in FM.
Study Design	This study design has two components: 1) a cross sectional assessment of brain chemistry, connectivity and response to pain in healthy controls and age- and sex-matched fibromyalgia patients, and 2) a longitudinal assessment of the same fibromyalgia patients randomized to either electro-acupuncture (EA) or mock laser acupuncture (ML).
Study Interventions	Electro acupuncture and mock laser acupuncture. Treatments will be delivered at 2x/week for 4 weeks, for a total of 8 treatments.
Study Duration	The study duration for healthy controls will be 1 week, with a 4 week screening window. The study duration for fibromyalgia patients will be up to 10 weeks: 4- week screening window prior to baseline; 1-week of baseline, 4 week treatment period, and 1 week of follow up.
Sample Size and Population	We will evaluate 40 healthy controls and 80 fibromyalgia patients (n=40 EA and n=40 ML). Demographics will be representative of the population of southeastern Michigan.
Statistical Analyses	
Cross-sectional analyses will include a comparison of FM patients with HC with respect to GABA, Glx and other neuroimaging biomarkers (t-tests, linear regression);
 
Longitudinal analysis will study treatment effects on within-patient change in neuroimaging biomarkers and changes in clinical pain (t-tests, linear regression with change as a response, linear mixed model with biomarker as a response); treatment and biomarker predictive effects at baseline on clinically relevant 50% reduction of pain as a binary response (logistic regression); the effects of treatment and biomarker baseline measurements on within-patient change in DMN-insula connectivity; biomarker mediation analysis for the treatment effect.
 
In order to screen neuroimaging biomarkers that respond to treatment (show reduced DMN-insula connectivity), interim testing for futility will be performed.
 
Reasons for missingness will be analyzed using multinomial logistic regression with treatment as one of the covariates. The results of formal missing data imputation by predictive-matching algorithms will be compared to the results of missing data exclusion in a sensitivity analysis.

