 - **Hypothesis 3:** EA will more readily reduce pain-evoked fMRI activation in the insula as compared to ML, which will not reduce pain-evoked fMRI activation. The change in pain will correlate with change in insula response to evoked pain for EA but not ML.
- ◆ **Aim 3. Evaluate the ability of altered neurocircuitry at baseline to predict clinical response to electro- and mock laser acupuncture**
- **Hypothesis 1:** FM patients with greater baseline DMN-insula positive correlation and SMN-insula anti-correlation will display greater clinical response to EA. There will be no predictive value for ML – which is an inert form of sham acupuncture with no somatosensory afference.
 - **Hypothesis 2:** FM patients with greater baseline insular Glx/GABA ratios will display greater clinical response to EA. There will be no predictive value for ML.
 - **Hypothesis 3:** FM patients with greater baseline pain-evoked insular activation will display greater clinical response to EA. There will again be no predictive value for ML.

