Change in pain-evoked fMRI activation will be correlated with the change in clinical pain. To do this evoked pain responses will be added as covariates into the linear mixed model regressing BPI pain on other covariates.

Mediation Analysis is similar to the one proposed for connectivity.

11.3. Aim 3: Evaluate the ability of altered neurocircuitry at baseline to predict clinical response.

This aim evaluates a *predictive* value of the neuroimaging biomarkers by studying whether their measurements at baseline correlate with pain responses to treatments.

Hypothesis 1: Greater baseline DMN-insula/S2 connectivity and SMN-insula/S2 anti-correlation, will display greater clinical response to EA vs. ML

We will use baseline estimates of DMN and SMN connectivity, taken from the dual regression ICA analysis, as independent variable in a multiple regression model with dependent variable set as the change score (post-therapy – baseline) for clinical pain (Brief Pain Inventory; BPI). Regression slopes will be contrast between different pairs (e.g. EA vs. ML) set in the same regression model. We will explore within-group correlations for individual therapies if the difference map for any two therapies is significant, at cluster corrected $p=0.05$.

Hypothesis 2: FM patients with greater baseline insular and S2 Glx/GABA ratios will display greater clinical response to EA as compared to ML.

An identical approach will be used as for hypothesis 1 above, but with Glx/GABA ratio as dependent variable.

Hypothesis 3: FM patients with greater baseline pain-evoked insular activation will display greater clinical response to EA as compared to ML.

An ROI analysis will determine baseline insula response to evoked pain. This parameter estimate will then be used as a dependent variable in an identical multiple linear regression approach, as detailed above.

Power. The expectations for correlations between the baseline measurements of biomarkers and clinical pain responses are set similar to the mechanistic setting. We expect to uncover correlations of 0.5 between measurements at baseline and the change in pain in response to treatment (mainly in the EA arm). We will have 94% power to detect such correlations.

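### The synopsis and Section 11.3 give different outcomes and models for baseline prediction of pain response, neither is named primary, and dichotomising would cost substantial power

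*Combined protocol and SAP*

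**What the plan says.** Section 2 (Synopsis, Statistical Analyses) gives a list of longitudinal analyses without aim labels. The item on baseline prediction of pain reads "treatment and biomarker predictive effects at baseline on clinically relevant 50% reduction of pain as a binary response (logistic regression").

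Section 11.3, which sets out Aim 3, uses another outcome and another model. Under Hypothesis 1 the baseline connectivity estimates enter "as independent variable in a multiple regression model with dependent variable set as the change score", and the outcome is change in BPI pain. The comparison of arms is then described: "Regression slopes will be contrast between different pairs (e.g. EA vs. ML) set in the same regression model". Section 9.3.3 likewise relates baseline evoked activation to change in clinical pain for Aim 3.

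The only Aim 3 power statement is in Section 11.3: "We expect to uncover correlations of 0.5 between measurements at baseline and the change in pain in response to treatment (mainly in the EA arm"), followed by "We will have 94% power to detect such correlations".

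In Section 11, a logistic model with pain response as outcome appears only in the Aim 2 mediation analysis (Section 11.2), at 50% and 30% reduction. No section ranks the two prediction analyses, gives an expected responder rate, or gives power for the binary outcome or for the EA-ML slope contrast.

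**The concern.** The two places answer the same question, whether baseline neuroimaging predicts who improves, with different outcomes and different models. If both stay open and unranked, either could be reported as the Aim 3 result after the data are seen, and this choice recurs for every biomarker (DMN and SMN connectivity, Glx/GABA ratio, evoked activation). If the binary version were taken as the main one, it would discard information in a trial with 40 patients per arm. A null result could then be read as absence of prediction when the test had little chance of finding it. The 94% would give no warning, because it belongs to neither the binary outcome nor the contrast between arms.

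**Working it through.** **Inputs from the documents.** Allocation: "80 fibromyalgia patients (n=40 EA and n=40 ML") (Synopsis). Correlation in EA: 0.5 (Section 11.3). Correlation in ML: 0, from Section 5, Aim 3, Hypothesis 1: "There will be no predictive value for ML – which is an inert form of sham acupuncture with no somatosensory afference".

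**Assumptions.** Two-sided 0.05, which is stated for Aim 1; Aim 3 gives only a cluster-corrected 0.05. One scalar biomarker, normal data, no dropout. Responder rates are assumed throughout. A responder is simulated by cutting the continuous change at a threshold; the plan's 50% is relative to baseline, so this is an approximation.

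**Step 1: reproduce the 94%.** For a slope in one arm of 40, the noncentrality is r√n / √(1 − r²) = 0.5 × 6.325 / 0.866 = 3.65 on 38 df, giving 94.5%. Bivariate-normal simulation gives 92.3%. Fisher z gives 0.549 × √37 = 3.34; 3.34 − 1.96 = 1.38; 91.6%. The stated figure therefore holds for a one-arm correlation with a continuous outcome.

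**Step 2: EA-ML contrast, continuous change.** Fisher z: 0.549 / √(1/37 + 1/37) = 0.549 / 0.2325 = 2.36; 2.36 − 1.96 = 0.40; 65.6%. Simulated treatment-by-biomarker interaction by least squares, equal outcome SD in both arms: 62-64%. If the residual SD is common instead: 69-70%.

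**Step 3: the same contrast after dichotomising.** The same simulated outcome was cut at assumed responder rates, and the interaction tested by logistic regression.

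| Responders EA/ML | Linear | Logistic, Wald | Logistic, likelihood ratio |
|---|---|---|---|
| 50/50% | 63% | 46% | 50% |
| 40/40% | 63% | 44% | 48% |
| 30/30% | 63% | 41% | 45% |
| 20/20% | 63% | 33% | 39% |
| 50/30% | 64% | 43% | 46% |
| 40/20% | 64% | 38% | 42% |
| 30/15% | 63% | 31% | 36% |
| 20/10% | 63% | 25% | 30% |

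**Step 4: rates implied by the plan's own pain effect.** Section 11.2 assumes a treatment effect of 2 on pain change, half of it mediated, a treatment effect of 3000 on connectivity, a connectivity SD of 4500 and a residual SD of 1.5. The biomarker coefficient is then 1/3000 and its contribution to the SD of pain change is 4500/3000 = 1.5. The total SD is √(1.5² + 1.5²) = 2.12. The arms differ by 2/2.12 = 0.94 SD, or by 2/1.5 = 1.33 SD if only the residual SD is used. With 30-70% EA responders, the ML rate is 7-34% at 0.94 SD and 3-21% at 1.33 SD. Power for the binary contrast is then about 10-47%.

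**Step 5: EA arm alone, logistic.** 66-77% at 30-50% responders and 45-65% at 15-20%, against the stated 94% for continuous change.

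**The case against.** The strongest reply is that there is no contradiction. The synopsis item carries no aim label, names treatment and biomarker effects but no interaction or slope contrast, and sits in a cumulative list. It may be an additional responder analysis, with Section 11.3 governing because it holds the detailed model and the power statement. This partly stands. A reader might infer that the synopsis prescribes a binary EA-ML interaction test for Aim 3 and that the power in Steps 3 and 4 is that of the planned analysis. The documents do not support that: the slope contrast is written only for the linear model. What remains is that the item's content is Aim 3's content, and if it is an addition, Section 11.3 omits its model, power and rank.

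Nor is the synopsis without continuous models. It lists linear regression with change as response for treatment effects, including on clinical pain, and baseline biomarker effects on change in DMN-insula connectivity. The narrower statement holds: it names no continuous model of pain change on baseline biomarkers.

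The 62-66% is also not the power of Hypothesis 1 exactly as written, which uses cluster-corrected maps. The drop from 94% to that range comes from moving from one arm to a contrast between arms, not from dichotomising.

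Finally, preferring continuous change is partly a judgement. The Aim 3 hypotheses speak of clinical response, and the synopsis regards a 50% reduction as clinically relevant. Section 11.3 also puts the mechanistic analysis ahead of the predictive one at the interim, which limits the weight of this point.

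**Conclusion.** The point holds as an unranked mismatch between the synopsis and Section 11.3. On the plan's correlations with 40 per arm, the EA-ML contrast has about 62-66% power on continuous change and roughly 25-50% after dichotomising at the rates in Step 3. If few ML patients respond, as the plan's own 2-point effect can imply, power can fall to about 10%. These figures assume one biomarker, uncorrected two-sided 0.05 and no dropout, and the binary range depends on responder rates that the documents do not supply. The direction does not: the logistic contrast was weaker in every scenario run. The 94% is not an arithmetic error; it answers a narrower question. The defect is worth correcting but does not invalidate the trial.

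**What to change.** State in Section 11.3 that the primary Aim 3 analysis is linear regression with BPI change as the dependent variable and baseline biomarker, treatment and their interaction as independent variables, for all three hypotheses. Section 11.3 should not simply be declared to govern as it stands. Hypotheses 2 and 3 claim the same approach as Hypothesis 1 but make the Glx/GABA ratio and the insula activation estimate the dependent variable, and that wording needs correcting. Align the synopsis, and list the 50% responder logistic model there and in Section 11.3 as supportive. Beside the 94%, say that it refers to a one-arm correlation, and give the power for the interaction.

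The cost is wording in the synopsis and Section 11.3, with no change to data collection or sample size. The downside is that the responder result, which is easier to interpret clinically, is no longer a headline test, though it can still be reported.

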3. SCHEDULE OF EVALUATIONS

3.1. Fibromyalgia Cohort

	Screening	Behavioral Session	Baseline MRI	Treatment Period	Behavioral Session	Follow-Up MRI
	Visit 0 Day -30 to 0	Visit 1 Day 0	Visit 2 Day 1-3	Visit 3-10 Day 4-32	Visit 11 Day 33-40	Visit 12 Day 34-43
Informed Consent	X					
Tender Point (1990 ACR FM Criteria)	X					
FM Survey Questionnaire (FSQ) Wolfe et al 2011 criteria for FM	X	X			X	
VAS – Pain (7day recall)	X					
FM Treatment History	X					
Medical History	X					
Vitals (Height/Weight)	X					
Urine Pregnancy Test	X	X	a		X	a
HADS	X				X	
PHQ-9 (suicidal ideation)	X	c		c	X	
Demographics	X					
Socio-demographics	X					
fMRI Screening Form		X			X	
Concomitant Medications	X	X	X	X	X	X
BPI – Severity/Interference	X	X	X		X	X
PROMIS – 29		X			X	
Perceptions of Bodily Sensations		X			X	
Pain Catastrophizing		X			X	
Credibility Scale				X	X	
PainDETECT		X			X	
Desire of Relief (DRF)		X			X	
Expected Relief Scale (ERS)		X				
MASQ (Cognition)		X			X	
Pittsburgh Sleep Quality Index (PSQI)		X			X	
VAS - Present Pain		X	X		X	X
Menstrual questionnaire		X			X	
Pain Assessment/Visual Stimulation Assessment	b	X			X	
After Cuff Questionnaire		X	X		X	X

Conditioned Pain Modulation (CPM)	b	X			X	
Neuroimaging ♦ Structural MRI ♦ Resting fcMRI ♦ Evoked Pain Test ♦ CPM (cuff) ¹ H-MRS ♦ Visual Stimulation			X			X
Randomization				X		
Treatment (EA / ML)				X		
Needling Sensations (MASS)				X		
Fibromyalgia Impact Questionnaire (FIQ-R)	X	X		X	X	
Harvard Food Diary (FFQ)		X				
Adverse Events		X	X	X	X	X
Debriefing						X

^a If not performed at behavioral session

^b Familiarization Only

^c Additional Monitoring for PHQ9 scores (10 – 14) – baseline behavioral and Treatment #3

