3.2. Controls

	Screening	Behavioral Session	Baseline MRI
	Visit 0 Day -30 to -0	Visit 1 Day 0	Visit 2 Day 1-3
Informed Consent	X		
Tender Point (1990 ACR FM Criteria)	X		
FM Survey Questionnaire (FSQ) Wolfe et al 2011 criteria for FM	X	X	
VAS – Pain (7-day recall)	X		
Medical History	X		
Vitals (Height/Weight)	X		
Urine Pregnancy Test	X	X	a
HADS	X		
PHQ-9 (suicidal ideation)	X	c	
Demographics	X		
Socio-demographics	X		
fMRI Screening Form		X	
Concomitant Medications	X	X	X
BPI – Severity/Interference	X	X	X
PROMIS – 29		X	
Perceptions of Bodily Sensations		X	
Pain Catastrophizing		X	
Credibility Scale			
PainDETECT		X	
Desire of Relief (DRF)			
Expected Relief Scale (ERS)			
MASQ (Cognition)		X	
Pittsburgh Sleep Quality Index (PSQI)		X	
VAS - Present Pain		X	X
Menstrual questionnaire		X	
Harvard Food Diary (FFQ)		X	
Pain Assessment/Visual Stimulation Assessment	b	X	
After Cuff Questionnaire		X	X

Conditioned Pain Modulation (CPM)	b	X	
Neuroimaging ♦ Structural MRI ♦ Resting fcMRI ♦ Evoked Pain Test ♦ CPM (cuff) ¹ H-MRS ♦ Visual Stimulation Assessment			X
Randomization			
Treatment (EA / ML)			
Needling Sensations (MASS)			
Adverse Events		X	X
Debriefing			

^a If not performed at behavioral session

^b Familiarization Only

^c Additional Monitoring for PHQ9 scores (10 – 14) – baseline behavioral

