8.1.2. Exclusion Criteria

Exclusion Criteria for Fibromyalgia Participants:

- Acupuncture within last 6-months.
- Presence of a known coagulation abnormality, thrombocytopenia, or bleeding diathesis that may preclude the safe use of acupuncture.
- Presence of a concurrent autoimmune or inflammatory disease such as rheumatoid arthritis, systemic lupus erythematosus, inflammatory bowel disease, etc. that causes pain or any other chronic pain condition with pain greater than FM pain.
- History of head injury with substantial loss of consciousness
- Peripheral neuropathy of known cause that interferes with activities of daily living.
- Routine daily use of narcotic analgesics, marijuana, or history of substance abuse.
- Stimulant medications, such as those used to treat ADD/ADHD (e.g., amphetamine/ dextroamphetamine [Adderall®], methylphenidate, dextroamphetamine), or the fatigue associated with sleep apnea or shift work (e.g., modafinil), are excluded.
- Concurrent participation in other therapeutic trials.
- Pregnant or nursing.
- Severe psychiatric illnesses (current schizophrenia, major depression with suicidal ideation).

- Active substance abuse disorder in the past 24 months as determined by subject self-report
- Use of PRN over the counter (OTC) pain medications (NSAIDs, etc.) on day of MRI scan.
- Use of PRN narcotic pain medication 48 hours prior to MRI scan.
- Contraindications to fcMRI, fMRI, or ¹H-MRS methods. These may include but are not limited to: surgical clips, surgical staples, metal implants, and certain metallic dental material. [Note: a more formal description of contraindications for MRI is present in our DSM Plan].
- Any impairment, activity or situation that in the judgment of the Study Coordinator or Principal Investigator that would prevent satisfactory completion of the study protocol. This includes unreliable, or inconsistent pain scores as deemed by the principal investigator.
- Current, habitual, or previous use within the last 12 months of artificial nails, nail enhancements, or nail extensions that cover any portion of either thumbnail. Exceptions, including brief and/or occasional use, may be permissible at the discretion of the principal investigator.

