9.4. Schedule of Assessments

The schedule of study procedures and assessments is tabulated in Section 3. The descriptions of the procedures to be performed at each visit are provided below.

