10.1 Safety Parameters

We will assess changes in fibromyalgia symptoms throughout the trial using the Fibromyalgia Impact Questionnaire-Revised (FIQ-R). FIQ-R symptom scores will be logged and reviewed in aggregate by the IMC annually. Significant changes in patient FIQ-R symptom scores will be logged and reported in aggregate to the IMC, IRB, and NCCAM annually. Other safety measures will include verbal contact with the patient throughout the trial. This will be in the form of patients’ response to the questions:

“Since your last acupuncture session, have you experienced a significant worsening change in any of the following?”

- (a) Nausea/Vomiting
- (b) Fainting
- (c) Localized skin infection or bleeding at the site of the treatment
- (d) Increased Pain other than the normal symptoms of fibromyalgia pain

There are no specific laboratory blood tests within this study. As such there will be no safety measures in place to monitor blood outcomes.

Suicidal ideation will be assessed at screening using the Patient Health Questionnaire (PHQ-9). Depression and Anxiety will be assessed at screening, baseline and follow-up. Subjects scoring between 10-14 on the PHQ-9 (“Moderately Depressed”) will be eligible to enroll but will require additional monitoring and will be asked to retake the PHQ-9 at the baseline behavioral visit (visit 1) and the third treatment visit (visit 5), in addition to the scheduled survey administration of visit 0 and visit 11. Subjects scoring between 15-19 (“Moderately Severe” depression) will be referred to the PI for a decision. Should they be enrolled in the study, they will also complete the PHQ-9 at visit 1 and visit 5. Any score above 20 will be considered “Severe” depression, and the subject will not be eligible. Any subject that reports a score of > 0 on question 9 (“Thoughts that you would be better off dead, or of hurting yourself”) of the PHQ-9 will be referred to support services offered by the University of Michigan Hospital System. Any subject deemed ineligible based on their PHQ-9 will be referred to a support services offered by the University of Michigan Hospital System.

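### Schedule note c gives the extra PHQ-9 only for scores 10–14, but Section 10.1 also requires it for enrolled subjects scoring 15–19; a score of exactly 20 has no rule

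*Combined protocol and SAP*

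**What the plan says.** The FM schedule (Section 3.1) lists the PHQ-9 for everyone at V0 and V11. At V1 and in the treatment period it carries only the mark c, explained as "Additional Monitoring for PHQ9 scores (10 – 14) – baseline behavioral and Treatment #3". In the controls schedule (Section 3.2) the PHQ-9 is at V0, with mark c at V1: "Additional Monitoring for PHQ9 scores (10 – 14) – baseline behavioral".

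Section 10.1 admits subjects scoring 10–14 and retests them at V1 and V5. For the next band it says "Subjects scoring between 15-19 (“Moderately Severe” depression) will be referred to the PI for a decision" and then "Should they be enrolled in the study, they will also complete the PHQ-9 at visit 1 and visit 5". The top band reads: "Any score above 20 will be considered “Severe” depression, and the subject will not be eligible". The same section sends to support services "Any subject that reports a score of > 0 on question 9", the self-harm item.

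Section 9.4 tells staff where the schedule is to be found: "The schedule of study procedures and assessments is tabulated in Section 3". The visit lists for V1 (Section 9.4.2) and for treatment visits (Section 9.4.4) do not name the PHQ-9. The exclusion lists in Section 8.1.2 contain no PHQ-9 limit.

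**The concern.** The schedule is what carries the safety text out at visit level, and here it is narrower than that text. The group it omits is the one with the higher depression scores. For those patients the self-harm item, which triggers referral, would not be put again until after treatment has ended.

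The second point is separate. Read literally, Section 10.1 gives no instruction for a total score of 20. A subject at 19 goes to the PI and a subject at 21 is ineligible, while a subject at 20 falls under neither rule.

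**Working it through.** **Score bands side by side**

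| PHQ-9 at screening | Note c (3.1, 3.2) | Section 10.1 |
|---|---|---|
| 10–14 | extra PHQ-9 | eligible, extra PHQ-9 |
| 15–19 | not mentioned | PI decides; extra PHQ-9 if enrolled |
| 20 | not mentioned | no rule |
| 21 and above | not mentioned | not eligible |

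The visits themselves agree. V3 to V10 are treatments 1 to 8, so V5 is the third treatment. The mismatch lies only in who is retested.

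**Number of PHQ-9s for an enrolled subject scoring 15–19**

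- FM patient: note c gives V0 + V11 = 2; Section 10.1 gives V0 + V1 + V5 + V11 = 4.
- Control: note c gives V0 = 1; Section 10.1 gives V0 + V1 = 2.

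**Time without a PHQ-9, FM patient scoring 15–19**

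Inputs from Section 3.1: V0 = day −30 to 0, V1 = day 0, V3–V10 = days 4–32, V11 = days 33–40.

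Counting both readings from V1:

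- Note c: V1 to V11 = 33 − 0 = 33 to 40 − 0 = 40 days.
- Section 10.1, with the eight treatments evenly spaced (assumed): spacing = (32 − 4)/7 = 4 days, so V5 = 4 + 2 × 4 = day 12. V1 to V5 = 12 days. V5 to V11 = 33 − 12 = 21 to 40 − 12 = 28 days. The longest gap is 21–28 days.
- Difference: 33 − 21 = 12 and 40 − 28 = 12 days.

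If V5 instead falls anywhere in treatment week 2 (days 11–17, assumed), the longest gap under Section 10.1 is max(V5, V11 − V5):

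- lowest: max(17, 33 − 17) = 17 days
- highest: max(11, 40 − 11) = 29 days

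The reduction against note c is then min(V5, V11 − V5). It runs from 11 days (V5 on day 11) to 17 days (V5 on day 17, V11 on day 40).

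Counting from V1 puts the two readings on a common start, but under note c no PHQ-9 is taken at V1. The true interval between administrations is V0 to V11, which is 33 days if screening is on day 0 and 40 + 30 = 70 days at most. Under Section 10.1, with screening on day −30 and V5 on day 12, the longest interval is the 30 days from V0 to V1.

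**The case against.** The case for leaving this as a minor editorial note runs as follows. Section 10.1 already contains the right rule, and note c does not say *only*. A patient scoring 15–19 enters by an individual PI decision under the same paragraph that orders the retest. Harm therefore requires staff to follow a footnote and overlook the governing text. Other checks remain: confirmation at screening that there is no active suicidal ideation, review of eligibility at V1 and V2, a statement in Section 10.1 that depression and anxiety are assessed at baseline, adverse events, and the FIQ-R. Screening and V1 may fall on the same day, in which case the V1 retest adds little. A score of 20 is a slip at one integer, and PI judgment could exclude such a subject.

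Much of this limits the weight of the point, and some of it stands. The consequence is a later PHQ-9, not the loss of all safety checks. For controls it is one questionnaire with no treatment to follow. Actual staff practice cannot be known, because the Manual of Operations, the Data Safety Monitoring Plan, the checklists and the text of Section 10.6 were not available for this review and may give the wider range or a rule for 20.

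It does not remove the conflict. The eligibility reviews and the general statement on depression name no instrument, and the schedule shows the HADS only at V0 and V11. The questions put to patients between acupuncture sessions cover nausea, fainting, skin problems and pain, not mood. The FIQ-R is there to detect worsening fibromyalgia. None of these is a PHQ-9 retest, and PI discretion is not a rule for a total score of 20. Even a correct manual would leave the protocol at odds with itself.

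**Conclusion.** Both parts hold. Note c in Sections 3.1 and 3.2 omits enrolled subjects scoring 15–19, whom Section 10.1 requires to be retested, and no visit list corrects it. Followed as written, note c halves the PHQ-9s for such an FM patient and leaves the self-harm item unasked from screening to V11. The gap estimates rest on assumed treatment dates. The number of subjects affected is not given and could be zero. Section 10.1 literally has no rule for a score of 20; that 20 or above was meant is an inference, though a likely one.

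No endpoint, sample size or error rate is touched. The point should still be corrected, because it concerns an operating safety instruction and an eligibility threshold.

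**What to change.** - In Sections 3.1 and 3.2, change the score range in note c to *10–19 (15–19 if enrolled by the PI)*.
- In Section 10.1, make the ineligible band *20 or above*, after the sponsor confirms that this is the intent.
- Preferably, add the same limit to both exclusion lists in Section 8.1.2. This is optional drafting, since Section 10.1 already states the ineligibility.
- Check that the Manual of Operations and the visit and eligibility checklists carry the same ranges.

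The cost is two footnote edits, a few words in Section 10.1 and, if adopted, one line per cohort in Section 8.1.2. No new instrument or visit is needed.
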